4.5.9. Physical and Neurological Examination Variables

Patients will have a physical examination including an examination of the knees, hips, and shoulders performed according to the Schedule of Events in [Appendix 11.1](#). The result for each body system is an outcome of normal or abnormal. Neurological evaluations of specific domains as listed in the protocol will be described as normal or abnormal.

4.5.10. Other Safety Variables

- Joint Pain Questionnaire:
 - Number of subjects with significantly worse joint pain in any joint at each scheduled visit
 - Number of subjects with significantly worse joint pain by joint at each scheduled visit
- Joint space width for the index joints as well as other knee or hip joints at each scheduled visit
- Joint replacement:
 - number and percentage of patients with joint replacement (all JRs)
 - time to joint replacement decision (all JRs)

4.6. Pharmacokinetic Variables

The Pharmacokinetic (PK) variable will be fasinumab concentrations in serum at specified sampling time points.

4.7. Anti-Drug Antibody Variables

Samples for Anti-Drug Antibody (ADA) evaluation will be collected at baseline and at subsequent study visits.

Anti-drug antibody variables will include ADA status (positive or negative) and titer as follows:

- Total subjects negative in the ADA assay at all time points analyzed
- Pre-existing immunoreactivity - a positive ADA response at baseline with all post-dose ADA results negative, or a positive ADA response at baseline with all post-dose ADA responses less than 9-fold over baseline titer levels.
- Treatment emergent - defined as any post-dose positive ADA response when baseline results are negative
 - Persistent - A positive result in the ADA assay detected in at least 2 consecutive post baseline samples separated by at least a 16-week post baseline period [based on nominal sampling time], with no ADA-negative results in-between, regardless of any missing samples
 - Indeterminate - A positive result in the ADA assay at the last collection time point analyzed only, regardless of any missing samples

- Transient - Not persistent or indeterminate regardless of any missing samples
- Treatment boosted - defined as any post-dose positive ADA response that is at least 9-fold over the baseline level when baseline is positive in the ADA assay
- Titer Values
- Titer category: low (titer <1,000); moderate ($1,000 \leq \text{titer} \leq 10,000$); high (titer >10,000)
- Neutralizing ADA activity for samples positive in the ADA assay

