9. In the event that a patient must undergo JR surgery during the treatment or follow-up periods, he or she will be discontinued from study drug and asked to return for a pre-operative visit, and for follow-up safety evaluations 4 weeks and 20 weeks after surgery (Table 5). The pre-operative visit should be completed before JR surgery if at all possible. Joint replacement questionnaires are Knee Society Score questionnaire for knee replacements or Harris Hip Score questionnaire for hip replacements.
10. To be performed only if postmenopausal status has to be assessed for female patients  $\leq 59$  years of age.
11. In the event of a positive serum pregnancy test result, the patient should be withdrawn from study drug and should be asked to return to the clinic for all remaining study visits per the visit schedule (see Section 5.3.2).
12. In the event of a positive urine pregnancy test result, the patient should have a serum pregnancy test with a negative result in order to continue study participation. If the serum pregnancy test is positive, the patient should be withdrawn from study drug and should be asked to return to the clinic for all remaining study visits per the visit schedule (see Section 5.3.2).
13. PK, ADA, and research samples may also be drawn at any scheduled visit or unscheduled visit if a patient experiences a treatment-related safety TEAE.
14. Historical radiographs may be acceptable as outlined in the study imaging acquisition guidelines.

Table 2: Schedule of Events – Week 20 Visit through Week 52 Visit

Study Week	Week 20 Clinic Visit	Week 24 Clinic Visit	Week 28 Clinic Visit	Week 32 Clinic Visit	Clinic Visits Between Week 36 and End of Treatment	Week 52 or End of Treatment Visit 	Early Termination/JR Pre-operative Visit
Visit Window	Q4W (±7 days)	(±7 days)	(±7 days)	(±7 days)	(±7 days)	(±7 days)	
Treatment:							
SC Study Drug Injection 	X	X	X	X	X 		
Dispense paracetamol/acetaminophen and NSAID medication	X	X	X	X	X		
Paracetamol/acetaminophen /NSAID accountability	X	X	X	X	X	X	X
Recording of rescue treatment use in diary 	X	X	X	X	X	X	X
Concomitant medications	X	X	X	X	X	X	X
Safety:							
Weight						X	X
Vital Signs 	X	X	X	X	X	X	X
Physical Examination	X	X	X	X	X	X	X
Electrocardiogram			X			X	X
Injection site evaluation	X	X	X	X	X		
Orthostatic blood pressure	X	X	X	X	X	X	X
Joint Pain Questionnaire	X	X	X	X	X	X	X
Survey of autonomic symptoms	X	X	X	X	X	X	X

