#### **6.2.7. Week 52 or End of Treatment Visit**

Assessments for the end of treatment visit at week 52 are outlined in the schedule of events (Table 2).

If treatment is stopped for patients (for example, due to conditions in Section 3.1 or Section 5.3.2.1 being met or for other reasons per the patient or investigator), patients should complete the end of treatment/week 52 assessments at their next scheduled visit. Patients who discontinue study drug should be encouraged to continue participation in the study. All subsequent visits should be conducted according to the schedule of events and all procedures should be completed, except for study medication administration. Imaging does not need to be repeated at a routine visit if all radiographs were conducted within 30 days and submitted for central reading.

Although patients are encouraged to continue all scheduled clinic visits, if they refuse to do so but are willing to provide safety follow-up over the phone, pertinent safety data should be collected.

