5.1.9. Analysis of Anti-Drug Antibody Data

The ADA variables described in Section 4.7 will be summarized using descriptive statistics by dose/cohort group in the ADA analysis set. Prevalence of treatment-emergent and treatment-boosted ADA will be assessed as absolute occurrence (N) and percent of patients (%), grouped by study cohorts. For treatment emergent ADA, occurrence (N) and percent of patients (%) with persistent, transient and indeterminate ADA will be reported. The influence of treatment-emergent or treatment-boosted ADA assay response on individual PK profiles may be evaluated.

Listings of ADA positivity and titers presented by patient, time point, and dose cohort/group will also be provided.

Correlation analysis of safety versus treatment-emergent ADA positivity status may be performed on the SAF. Assessment will focus on the following safety events:

- Hypersensitivity (SMQ: Hypersensitivity [Narrow])
- Anaphylaxis (SMQ: Anaphylaxis[Narrow])

Number (%) of patients with the above-mentioned safety events may be summarized by treatment-emergent ADA positivity status, during the TEAE period.

In addition, correlation analysis of key efficacy endpoints versus treatment-emergent ADA status in patients who discontinued due to lack of efficacy may be summarized.

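### SAP 4.7 counts some patients who are still ADA-positive at their last sample as Transient, because Transient is a bare remainder and Indeterminate covers only a sole last positive

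*SAP*

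**What the plan says.** The parent category in SAP 4.7 is "Treatment emergent - defined as any post-dose positive ADA response when baseline results are negative". It has three sub-categories.

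- Persistent requires "A positive result in the ADA assay detected in at least 2 consecutive post baseline samples separated by at least a 16-week post baseline period". Spacing is judged by the planned sampling weeks, and a negative sample between the two positives breaks the pair; missing samples do not.
- The Indeterminate category is worded as "A positive result in the ADA assay at the last collection time point analyzed only, regardless of any missing samples".
- The remaining category reads "Transient - Not persistent or indeterminate regardless of any missing samples".

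SAP 5.1.9 uses the split once, for treatment-emergent ADA: "occurrence (N) and percent of patients (%) with persistent, transient and indeterminate ADA will be reported". Protocol 8.6 and 9.5.5 do not contain the split, so neither clarifies it.

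Protocol Tables 1, 2 and 4 place post-baseline ADA samples at week 16, week 32, week 52 or end of treatment, and 24 weeks after the last dose (week 72). A sample is also taken at an early-termination or joint-replacement pre-operative visit from week 20 onwards. Two provisions allow closer spacing. After an early stop, "patients should complete the end of treatment/week 52 assessments at their next scheduled visit" (Protocol 6.2.7). In addition, "PK, ADA, and research samples may also be drawn at any scheduled visit or unscheduled visit if a patient experiences a treatment-related safety TEAE" (Protocol Table 1 footnotes, repeated under Tables 2 and 4).

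**The concern.** A reader takes a transient antibody response to be one that was seen and then disappeared. The SAP's category carries no such condition. The rule also orders the evidence the wrong way round. A patient whose single positive is the last sample is Indeterminate, while a patient positive at week 16 and again, without interruption, at a last sample in week 20 to 28 is Transient. The second patient has more evidence of a continuing response and gets the label that suggests it resolved.

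The misplacement runs in one direction: unresolved or recurrent positivity can enter the Transient count. What is at stake is how one reported safety table is read.

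**Working it through.** The plan states no figure on this point, so there is nothing to reproduce. The check is to apply the three definitions literally, in order, to every positive/negative pattern.

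**Inputs.** Scheduled post-baseline samples at weeks 16, 32, 52 and 72 (Protocol Tables 1, 2 and 4); the three definitions in SAP 4.7. An early end-of-treatment sample is placed at its actual week. This follows SAP 6.4, which maps such visits by study day.

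**Scheduled gaps.** 32 − 16 = 16 weeks; 52 − 32 = 20; 72 − 52 = 20. All are at least 16, so two successive scheduled positives are always Persistent.

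**Full schedule.** Four samples give 2⁴ = 16 patterns: 1 all negative, 8 Persistent, 1 Indeterminate, 6 Transient. The 8 that end positive are:

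| Wk 16 | Wk 32 | Wk 52 | Wk 72 | SAP label |
|---|---|---|---|---|
| + | + | + | + | Persistent |
| + | + | − | + | Persistent |
| + | − | + | + | Persistent |
| − | + | + | + | Persistent |
| − | − | + | + | Persistent |
| − | − | − | + | Indeterminate |
| + | − | − | + | Transient |
| − | + | − | + | Transient |

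This gives 5 Persistent, 1 Indeterminate and 2 Transient.

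**Week 16, then a last sample at week 20, 24 or 28.** The gap is 4, 8 or 12 weeks, below 16. Of the 2 patterns ending positive, (−,+) is Indeterminate and (+,+) is Transient.

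**Weeks 16 and 32, then a last sample at week 36, 40 or 44.** The last gap is again 4, 8 or 12 weeks. Of the 4 patterns ending positive:

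- (+,+,+) is Persistent, because weeks 16 and 32 already qualify;
- (−,−,+) is Indeterminate;
- (−,+,+) is Transient, with no negative after the first positive;
- (+,−,+) is Transient, with an intervening negative.

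So the uninterrupted case needs week 16 to be negative or missing.

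**Scheduled samples with missing values allowed.** 6 of 40 patterns ending positive are Transient, for example (+,−,+,missing).

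**Sensitivity to wording.** The 16-week separation can be read as applying to two adjacent positives or to the span of an unbroken run. The results above are the same under both readings. With one extra sample at week 20, a single pattern that ends positive, (+,+,+,−,+) at weeks 16, 20, 32, 52 and 72, changes label: Persistent under the run reading, Transient under the adjacent one.

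**After redefinition.** If Transient requires a negative last sample, 0 of the 8 full-schedule patterns ending positive are Transient. The split becomes 5 Persistent and 3 Indeterminate.

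**The case against.** The case for leaving the text alone has several parts.

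- **Stopping drug is not leaving the study.** Protocol 5.3.2 and 6.2.7 ask patients who stop to keep attending, so later ADA samples are planned and an early end-of-treatment sample is usually not the last. This stands: the uninterrupted route needs the patient also to leave follow-up. A reader might infer that the problem falls on early discontinuers as a group; the documents do not support that. The route with an intervening negative can occur in patients who complete everything.
- **Intermittent positivity may fairly be called transient.** In (+,−,−,+) and (−,+,−,+) the first response did go away, and the SAP defines its own term. This has some force as a convention. It does not explain why a patient positive on two consecutive samples, the last included, is Transient while a patient with one last positive is Indeterminate.
- **The word restricting Indeterminate to the last time point may have been meant loosely.** If so, the text should say it; a programmer coding what is written gets the labels above.
- **The consequence is small.** This stands. A reader might infer that the primary safety endpoint is affected, since it names anti-fasinumab antibody formation. It is not: that component is an incidence, and sub-classifying the positives cannot change it. The possible safety, PK and efficacy assessments in SAP 5.1.9 use treatment-emergent or treatment-boosted status, not persistence.
- **The planned listings of positivity and titer by patient and time point would show each case.** True, but a summary table should not need a listing to correct its labels.

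**Conclusion.** The definitions should be corrected; the consequence is limited. As written, SAP 4.7 puts some treatment-emergent patients with a positive last sample into Transient by the two routes shown. It does not do so for all such patients.

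The enumeration shows which result patterns are mislabelled, not how often. A reader might take 2 of 8, or 2 of 4, as a share of patients. That would be wrong: counting patterns gives every pattern equal weight, and the documents supply no ADA incidence or pattern frequencies. The number of patients affected cannot be derived.

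The conclusion assumes that the Indeterminate definition is applied literally and that early end-of-treatment samples are timed by study day. The full-schedule result does not depend on the second assumption. The effect is confined to the descriptive N (%) for the three sub-categories in SAP 5.1.9.

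**What to change.** In SAP 4.7, keep Persistent unchanged and replace the other two definitions:

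- Indeterminate: treatment-emergent, not persistent, last analysed sample positive, whether or not earlier samples were positive.
- Transient: treatment-emergent, not persistent, last analysed sample negative.

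The three categories remain exhaustive and mutually exclusive. The cost is two lines of SAP text and the matching code, with no new data. The downside is that the Transient count may fall and the Indeterminate count rise.

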5. STATISTICAL METHODS

For continuous variables, descriptive statistics will include the following: the number of patients reflected in the calculation (n), mean, median, standard deviation (SD), minimum, maximum, and the first and third quartiles (Q1 and Q3).

For categorical or ordinal data, frequencies and percentages will be displayed for each category.

5.1. Statistical Methods for Long-Term Safety Study

5.1.1. Demographics and Baseline Characteristics

Demographic and baseline characteristics will be descriptively summarized by treatment group, combined fasinumab, and overall based on the FAS-LTS. Parameters to be summarized include those described in Section 4.1.

5.1.2. Medical History

Medical history will be descriptively summarized by treatment group, combined fasinumab and overall for the FAS-LTS. Summaries will show patient counts (percentages) by primary SOC and PT. The tables will be sorted by decreasing frequency of primary SOC in the overall group. Within each primary SOC, PTs will be sorted by decreasing frequency in the overall group.

5.1.3. Prior / Concomitant Medications

Prior Medications

All prior medications, dictionary coded by WHO, will be descriptively summarized by treatment group, and combined fasinumab based on the FAS-LTS. Summaries will present patient counts (and percentages) for all prior medications, by decreasing frequency of the overall group incidence of ATC followed by ATC level 2, ATC level 4 and preferred term. In case of equal frequency across anatomic or therapeutic categories, alphabetical order will be used. Patients will be counted once in each ATC category (anatomic or therapeutic) linked to the medication but may be counted several times for the same medication.

Concomitant Medications

All concomitant medications, dictionary coded by WHO, will be descriptively summarized by treatment group, and combined fasinumab based on the SAF-LTS. Summaries will present patient counts (and percentages) for the concomitant medication groups described in Section 4.3 for all concomitant medications, by decreasing frequency of the combined fasinumab group incidence of ATC followed by ATC level 2, ATC level 4 and preferred term. In case of equal frequency across anatomic or therapeutic categories, alphabetical order will be used. Patients will be counted once in each ATC category (anatomic or therapeutic) linked to the medication, hence may be counted several times for the same medication.

The following will be summarized:

- Prior Medications
- Concomitant medications
- Post-treatment medications
- On-study (Concomitant + Post-Treatment) Medications

When medication start/end date is missing, the rules for determining whether a medication is prior, concomitant, or post-treatment, are specified in Section 6.3.

5.1.4. Prohibited Medications

Number and percentage of patients with prohibited medications will be descriptively summarized by treatment group, and combined fasinumab based on the SAF-LTS. The tables will be sorted by decreasing frequency of ATC Level 2, ATC Level 4, and preferred term in the combined fasinumab group.

The number of patients with NSAID use during treatment period 1 will be summarized by treatment group, and combined fasinumab. Additionally, the number of patients with more than the limited amount of NSAID use during treatment period 2 will be summarized by treatment group, and combined fasinumab for patients in the SAF-LTS.

Total NSAIDs-use days during each treatment period and follow-up (before AA for patients with AA) will be summarized by treatment group, and combined fasinumab for patients in the SAF-LTS. Additionally, days from last study drug dose to first NSAID dose will be summarized by treatment group, and combined fasinumab for patients in the SAF-LTS.

5.1.5. Patient Disposition

The disposition of patients in the study will be summarized by treatment group, combined fasinumab and overall for FAS-LTS.

5.1.5.1. Screening Disposition

Percentages will be calculated using the number of screened patients as the denominator.

- Screened patients (defined as having signed the ICF).
- Patients randomized (defined in the protocol as having received a randomization number per IVRS).
- Patients did not meet inclusion/exclusion criteria but randomized (if applicable).
- Patients treated but not randomized (if applicable).

- Screen Fail patients. Reason for screen failure will be provided.

5.1.5.2. LTS study Disposition

- Unless otherwise noted, percentages will be calculated using the number of patients in FAS-LTS as the denominator. This will be summarized by treatment group, combined fasinumab, and overall for the LTS study. Kaplan-Meier plot of time to treatment discontinuation will be provided. Summaries will provide the frequency (and percentage as applicable) of patients that met the criteria for the following variables:
- Patients randomized (defined as having received a randomization number). This row will reflect grouping based on randomization assignment.
- Patients randomized but not treated. This row will reflect grouping based on randomization assignment.
- Patients randomized and treated.
- Patients who completed the study, patients who withdrew from the study and reason for study withdrawal.
- Patients who completed study treatment, patients who discontinued treatment and reason for treatment discontinuation.

5.1.5.3. Analysis Set

Summary of the number (and percentage) of patients in each analysis set) will be by treatment group, combined fasinumab, and overall for the LTS.

Additionally, the following listings will be provided (if applicable):

- Listing of Patients Treated but not Randomized.
- Listing of Patients Randomized but not Treated.
- Listing of Patients Randomized but not Treated with the Randomized treatment.
- Listing of Patient Disposition for all Randomized Patients.
- Listing of Screening Failures and reasons for all screen failed patients.

5.1.6. Extent of Study Treatment Exposure and Compliance

The analysis population for the entire LTS study is based on the SAF-LTS.

5.1.6.1. Measurement of Treatment Compliance

Compliance with protocol-defined investigational product will be calculated by treatment group and combined fasinumab as follows:

- $(\text{Number of actual injections of study drug during the LTS study exposure period}) / (\text{Number of planned injections of study drug during the LTS study exposure period on or before the time that the patient discontinues from the treatment phase of the study}) \times 100\%$

Treatment compliance will be presented by descriptive statistics as well as the number (%) of patients who have:

- 1, 2, 3, 4, 5, 6, 7, 8, 9, 10, 11, and 12 SC injections (for the entire LTS study)

5.1.6.2. Exposure to Investigational Product

The treatment exposure to fasinumab and placebo SC doses will be calculated as:

- $(\text{Date of last study drug dose} - \text{date of first study dose}) + 28$

The duration of exposure in will be summarized for each treatment group using the number of patients (n), mean, standard deviation, median, Q1, Q3, minimum, and maximum.

The number (%) of patients with exposure duration periods will be presented by specific time periods. The time periods of interest are specified as: ≥ 1 day, ≥ 29 days, ≥ 57 days, ≥ 85 days, ≥ 113 days, ≥ 141 days, ≥ 169 days, ≥ 197 days, ≥ 225 days, ≥ 253 days, ≥ 281 days, ≥ 309 days, ≥ 337 days

5.1.6.3. Length of Study Observation

The length of the observation period (days) will be calculated as:

- $(\text{Date of last study visit [up to End of Follow-up Clinic Visit]} - \text{date of first study drug dose}) + 1.$

The length of the total study observation period (days) will be calculated as:

- $(\text{Date of last study visit [up to End of Study Phone call]} - \text{date of first study drug dose}) + 1.$

The observation duration will be summarized for each treatment group using the number of patients (n), mean, standard deviation, median, Q1, Q3, minimum, and maximum.

The number (%) of patients with observation periods will be presented by specific time periods. The time periods of interest are specified as: ≥ 1 day, ≥ 29 days, ≥ 57 days, ≥ 85 days, ≥ 113 days, ≥ 141 days, ≥ 169 days, ≥ 197 days, ≥ 225 days, ≥ 253 days, ≥ 281 days, ≥ 309 days, ≥ 337 days, ≥ 365 days, ≥ 393 days, ≥ 421 days, ≥ 505 days, ≥ 701 days

5.1.6.4. Protocol Deviations

All major and minor protocol deviations have been collected and reviewed on an ongoing basis throughout the study as described in the Protocol Deviation Definitions Document (PDDD).

Protocol deviations will be summarized for patients incurring any major deviation by count and percentage, and patients incurring each type of major deviation by count and percentage for FAS-LTS.

A patient listing of all major and minor protocol deviations will be provided.

